### c. Procedure-related serious adverse events [Time Frame: through post-operative follow-up]

Case-report forms will include collection of data for adverse events including, but not limited to, mortality, myocardial infarction, tamponade, bleeding, deep wound infection, stroke, and pericarditis. While patients will not be required to receive a post-operative echocardiogram, those who do for standard of care purposes will have that data collected in the CRF.

## Statistical Methods

We developed the statistical approach and determined sample size with the collaboration of [name], a biostatistician in the University of Utah Study Design and Biostatistics Center. We have a long history of collaborations with [name].

(Aim 1). The incidence of adverse events (AEs) will be reported as percentages, with two-sided 95% confidence intervals. Statistical comparisons of AEs between the AM treatment and the control group will be made using a chi-square, or Fisher's exact test, as appropriate (based on the minimum expected cell frequencies). These statistical comparisons, however, are known to be underpowered, and so the p values will be basically just descriptive. The user experience, such as ease of handling and applicability, will be reported descriptively.

(Aims 2 and 3). Since randomization will be used, simple significance tests should be sufficient, as the need to control for confounding will be essentially eliminated. Statistical comparisons of binary outcomes will be compared using a chi-square or Fisher's exact test, as appropriate. Statistical comparisons of continuous outcomes will be made using a two-sample t-test. If trends are observed in the expected direction (AM appears to be efficacious), this will support a conclusion of feasibility that justifies advancing to the next, larger study. Descriptive statistics will be reported to aid in sample size determination of the next, larger study.

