## Background and Significance

Post-operative atrial fibrillation (POAF) is a common and potentially serious complication following cardiac surgery. Between 20-50% of patients experience atrial fibrillation (AF) often during the first week after surgery. POAF is not a benign condition. It is associated with a two- to four-fold increased risk of readmissions, renal failure, stroke, pacemaker implants, and bleeding. In addition, POAF carries a two-fold increase in all-cause 30-day mortality. POAF has long term implications. Of cardiac surgery patients who experience new onset AF, 18% had late AF at 1 year follow up, while 36% had AF at 5 years, and 55% had AF at 10 years. Accordingly, POAF may be an indication of an underlying myocardial substrate and represent a risk factor for developing sustained AF, rather than an unrelated post-surgical complication. POAF is not limited in its impact during the perioperative period, but rather, is associated with 4-fold risk of stroke and a 3-fold increase in all-cause mortality at 1 year. Patients who develop POAF incur on average \$10,000-\$20,000 in additional hospital treatment costs, 12-24 hours of prolonged ICU time, and an additional 2 to 5 days in the hospital. Indeed, the socioeconomic impact is profound. Healthcare costs related to the care of patients with POAF in the US are estimated at over \$1 billion annually.

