## Specific Aims

Cardiopulmonary bypass triggers a systemic and localized inflammatory response which has been shown to serve as a trigger for POAF onset. Some evidence further suggests that releasing the heart from its natural pericardial restraint can augment this response.

The Cell Therapy and Regenerative Medicine Program (CellReGen) at the University of Utah manufactures sterile AM for human use which is currently used to enhance wound healing, particularly in burn patients. Early investigation by our basic science laboratory has demonstrated that placement of AM on rat hearts after myocardial infarction can decrease myocardial scarring.

The primary objective of this research endeavor is to determine the safety of AM as a pericardial substitute in cardiac surgery with a secondary aim as to whether application of AM decrease the incidence of POAF following cardiac surgery. We hypothesize that application of AM at the time of cardiac surgery will decrease inflammation and the subsequent substrate for the development of POAF. In order to test this hypothesis, we

propose a pilot clinical trial in patients undergoing cardiac surgery at the University of Utah with the following specific aims:

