**Aim 2: Compare incidence of POAF for until post-operative follow-up**

The incidence and burden of POAF will be assessed using 24 hour telemetry during hospital stay as well as a daily EKG reading at home between discharge and post-operative follow-up appointment.

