### b. Monitoring of POAF (Time frame: from discharge through surgical follow-up appointment)

The incidence of POAF would be quantified for the period between the patient's discharge and their return to clinic for the surgical post-operative follow-up appointment. Patients will be on continuous telemetry while in the hospital. They will be discharged home with a KardiaMobile EKG device, and asked to record a 6-lead EKG once daily during this period between discharge and their follow-up appointments. The number of occurrences and duration of any POAF episodes (atrial fibrillation burden) will be recorded and treated according to standard clinical practices.

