## Sample Size Justification

For a pilot study, where small sample sizes are used, a sample size of  $n = 12$  per group is recommended, because the standard error of the mean is known to decrease rapidly for each additional subject up to  $n = 12$ , after which diminishing returns sets in, with each additional subject having a noticeably smaller contribution to the reduction in the standard error. This means that statistical power is greatly improved by increasing the sample size up to  $n=12$ , but it takes substantial increases in the sample size beyond that to impact power appreciably. For the efficacy aims (Aims 2 and 3), then,  $n=12$  per group is sufficient to detect trends from statistical comparisons without unduly increasing the size of the study. We will use  $n=20$  per group, however. This provides 80% power to detect a 0.80 SD difference in means, using a two-sided alpha 0.10 comparison. If the effect is large, then, we will likely see at least marginally statistical significant differences. Statistical significance is not needed, however, for a pilot feasibility study, as only a trend in the expected direction is required. Also, the  $n=20$  per group is large enough to provide reasonably stable estimates of means and standard deviations for sample size determination for the next, larger study. (Aim 1) The  $n=20$  per group provides a reasonable opportunity to detect adverse events (AE) in the AM treatment group. Intuitively, if the AE is common, 1/20 or 5%, it seems that at least 20 subjects should be used to detect 1 event (1 out of 20). The exact probability is determined by the binomial probability formula,

$$\begin{aligned} & \text{Prob(at least 1 event is observed | probability is 1/20)} \\ &= 1 - \binom{N}{n} p^n (1-p)^{N-n} = 1 - \binom{20}{0} p^0 (1-p)^{20-0} = 1 - (1)(1)(.95)^{20} = 1 - .358 \\ &= .64 \text{ or } 64\% \end{aligned}$$

So, if the probability of an AE is 1/20, or 5%, we will have a 64% probability of observing at least one AE in our AM treatment group. To increase the probability to 90% would require  $n = 45$  per group, which is unreasonable. That is, it is more ethical to use fewer subjects at this stage of the product development, in case the risk of an AE is even higher. Furthermore, if the risk of the AE is very high 1/10, or 10%, we have an 88% probability of observing an AE with our  $n=20$ .

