## Future Implications

This pilot project is a multidisciplinary collaboration with implications for our team and the University of Utah. This pilot project is aimed at providing an initial data and trend for the use of AM as a pericardial substitute to decrease POAF.

- Besides mitigating inflammation, AM has been shown to decreased fibrosis. It is hard to quantify and characterize adhesions in clinical setting. Following a positive signal from this pilot study future animal studies looking for biochemical markers of fibrosis, devising MRI protocols to determine the severity of adhesions and quantifying adhesions at the time of re-do surgery would be undertaken. This has far reaching implications as increasing number of elderly population are undergoing re-operative surgeries and in the pediatric population, cardiac surgeons routinely perform surgery on children with previous sternotomies. Re-do sternotomy although becoming safer, is associated with increased morbidity and mortality.
- Our team is involved in a trial with CVRTI on identifying cardiac surgery patients with increased atrial substrate remodeling based on intraoperative atrial conduction characteristics recorded at time of cardiac surgery together with clinical and MRI factors to predict POAF. The intraoperative electrical mapping data utilizing a custom-made array along with clinical factors would help us to develop a real time diagnostic tool to predict POAF in cardiothoracic patients. The preliminary data from this pilot project utilizing the AM as an anti-inflammatory agent combined with our ongoing research exploring the substrate for AF, would have important therapeutic implications.
- From a commercialization standpoint, translation of positive findings to a larger scale would provide the CTRM and the University of Utah with a transformative pericardial substitute that could be applied to over 500,000 patients/year receiving heart surgery

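### Aim 2 counts POAF from the hospital stay onward, but the monitoring section counts it only from discharge, which would drop in-hospital AF from the efficacy comparison

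*Combined protocol and SAP*

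**What the plan says.** Aim 2 states that the incidence and burden of POAF "will be assessed using 24 hour telemetry during hospital stay as well as a daily EKG reading at home" until the post-operative visit. Its window therefore includes the hospital stay.

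Follow-up Evaluation, section b, sets a narrower window twice. Its heading reads "Time frame: from discharge through surgical follow-up appointment". Its first sentence begins "The incidence of POAF would be quantified for the period between" and names discharge and the return to clinic as the two ends. The same section also plans continuous telemetry in hospital. It closes by recording the number and duration of any POAF episodes, without saying whether in-hospital episodes enter the incidence.

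On timing, Background and Significance says: "Between 20-50% of patients experience atrial fibrillation (AF) often during the first week after surgery".

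On use of the result, the Statistical Methods paragraph for Aims 2 and 3 says: "If trends are observed in the expected direction (AM appears to be efficacious), this will support a conclusion of feasibility that justifies advancing" to a larger study. It adds that descriptive statistics will feed that study's sample size. Sample Size Justification says: "Statistical significance is not needed, however, for a pilot feasibility study, as only a trend in the expected direction is required". Confidence intervals are specified for Aim 1 event rates but not for the POAF comparison.

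**The concern.** The two windows give different outcomes. A patient who has AF on day 3 in hospital and sinus rhythm on every home recording is a case under Aim 2 and not a case under section b. The protocol itself says AF often occurs in the first week, so such patients may be common.

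Three things depend on the choice: the Aim 2 comparison between arms, the direction of the trend that is meant to support a larger study, and the POAF rates passed on for that study's sample size. With fewer events counted, a true benefit is less likely to show as a favourable direction and ties become more frequent. A control rate that omits in-hospital AF would also misstate the problem that the next trial is meant to address.

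**Working it through.** **The plan's own figure.** The only efficacy power statement is for means: 20 per group, a 0.80 SD difference, two-sided alpha 0.10, 80% power. The two-sample t-test gives 79.9%, so it reproduces. It does not bear on POAF incidence, for which the plan gives no power.

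**The texts side by side.**

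| Place | Window for POAF incidence |
|---|---|
| Aim 2 | Hospital stay (telemetry) plus home period (daily EKG) |
| Follow-up Evaluation b, heading | Discharge to follow-up visit |
| Follow-up Evaluation b, first sentence | Discharge to return to clinic |
| Follow-up Evaluation b, later sentences | Telemetry in hospital and recording of any episodes; incidence window not widened |

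**What the narrower window could cost.** Inputs:

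- n = 20 per arm, from the protocol.
- Control POAF rate p = 30% for the main case, inside the 20-50% that the Background gives for cardiac surgery generally. The exclusion criteria could lower it.
- A halving on AM, to p/2 = 15% (assumed).
- s = share of POAF patients whose AF occurs only before discharge (assumed, equal in both arms; not in the documents).
- Trend = strictly fewer AM cases than control cases (assumed; the plan does not define it).

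Counts are X_AM ~ Binomial(20, (p/2)(1 - s)) and X_C ~ Binomial(20, p(1 - s)), independent. P(trend) is the sum of P(X_AM = a) P(X_C = c) over all a < c. P(tie) is the sum over a = c.

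| s | Expected cases, control v AM | P(trend) | P(tie) |
|---|---|---|---|
| 0 (full window) | 6 v 3 | 83% | 8% |
| 25% | 4.5 v 2.25 | 77% | 11% |
| 50% | 3 v 1.5 | 69% | 16% |
| 75% | 1.5 v 0.75 | 56% | 26% |
| 90% | 0.6 v 0.3 | 36% | 48% |

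For example, at s = 50% the expected control count is 20 × 0.30 × 0.5 = 3.

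With a halving at the ends of the Background's range, P(trend) for s = 0, 25%, 50%, 75% and 90% is:

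- control rate 20%: 75%, 69%, 61%, 47%, 28%
- control rate 50%: 93%, 88%, 80%, 66%, 47%

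These figures ignore AF missed between once-daily home recordings.

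**How much a direction tells the reader, even in the full window.** With no effect and a common rate of 20-50%, AM still has fewer cases in 42-44% of trials. Take 3/20 on AM against 6/20 on control, the expected counts above. The difference is 0.15 - 0.30 = -0.15. The Wilson 95% limits are 0.052 to 0.360 and 0.145 to 0.519. Newcombe's limits are then:

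- lower: -0.15 - √[(0.15 - 0.052)² + (0.519 - 0.30)²] = -0.39
- upper: -0.15 + √[(0.360 - 0.15)² + (0.30 - 0.145)²] = +0.11

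That is -15 points, 95% CI -39 to +11.

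**The case against.** The best defence is that section b does not discard in-hospital AF. It plans continuous telemetry and records any POAF episodes, and Aim 2 counts the stay. The loss arises only if an analyst takes the heading and first sentence of section b as the definition. It is also right that first week does not mean before discharge, that no length of stay is given, and that the loss is modest at a 25% share (83% to 77%). All of this stands as a limit on size. It does not remove the conflict, because nothing in section b extends the incidence window and no sentence says which section governs.

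A reader might also infer that the advance statement is defective because it names no deciding outcome and leaves out Aim 1, although Specific Aims says: "The primary objective of this research endeavor is to determine the safety of AM as a pericardial substitute in cardiac surgery". The documents do not support calling that an error. The statement says trends will support feasibility, not that they suffice whatever the safety results. It sits in the paragraph on Aims 2 and 3, directly after a separate Aim 1 analysis with confidence intervals. The remark that only a trend is needed contrasts trend with significance, not with safety. On the outcome, Future Implications points to POAF: "This pilot project is aimed at providing an initial data and trend for the use of AM as a pericardial substitute to decrease POAF". But the only power figure is for means, and the hypothesis runs through inflammation, so ranking POAF above the markers is a debatable choice. A pilot may also favour sensitivity, and this one claims no error control for the trend.

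**Conclusion.** The inconsistency is real. Aim 2 and Follow-up Evaluation b define POAF incidence over different periods, and following section b as written would drop in-hospital AF from the comparison, the trend and the planning estimates. This should be corrected before analysis.

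The direction of the effect is the same at every share examined. Its size is illustrative: at 30% v 15%, the chance of a favourable trend falls from 83% to between 77% and 36% as the assumed pre-discharge share goes from 25% to 90%. Nothing in the documents fixes that share, so the 36% should not be read as a forecast. The result also rests on the assumed halving, an equal share in both arms, and a trend read as strictly fewer AM cases. The missing confidence interval for POAF is a smaller, related reporting gap.

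**What to change.** 1. In Follow-up Evaluation b, heading and first sentence, define POAF incidence and burden from surgery to the follow-up visit, using hospital telemetry plus home EKG, in line with Aim 2. Report the in-hospital and post-discharge parts separately.
2. In Statistical Methods (Aims 2 and 3), report the POAF risk difference with its 95% CI beside any trend, as confidence intervals are already planned for Aim 1 event rates.

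Both are text changes. Telemetry and home EKG are already planned, so no patients, visits or assays are added. The downside is that in-hospital AF may dominate the combined incidence, which is why the two parts are shown separately. The change does not lower the 42-44% chance of a favourable direction when there is no effect; the interval makes that uncertainty visible.

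Naming the outcome that carries the advance statement, and saying that Aim 1 results are weighed before advancing, would be optional clarifications.

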## Sample Size Justification

For a pilot study, where small sample sizes are used, a sample size of  $n = 12$  per group is recommended, because the standard error of the mean is known to decrease rapidly for each additional subject up to  $n = 12$ , after which diminishing returns sets in, with each additional subject having a noticeably smaller contribution to the reduction in the standard error. This means that statistical power is greatly improved by increasing the sample size up to  $n=12$ , but it takes substantial increases in the sample size beyond that to impact power appreciably. For the efficacy aims (Aims 2 and 3), then,  $n=12$  per group is sufficient to detect trends from statistical comparisons without unduly increasing the size of the study. We will use  $n=20$  per group, however. This provides 80% power to detect a 0.80 SD difference in means, using a two-sided alpha 0.10 comparison. If the effect is large, then, we will likely see at least marginally statistical significant differences. Statistical significance is not needed, however, for a pilot feasibility study, as only a trend in the expected direction is required. Also, the  $n=20$  per group is large enough to provide reasonably stable estimates of means and standard deviations for sample size determination for the next, larger study. (Aim 1) The  $n=20$  per group provides a reasonable opportunity to detect adverse events (AE) in the AM treatment group. Intuitively, if the AE is common, 1/20 or 5%, it seems that at least 20 subjects should be used to detect 1 event (1 out of 20). The exact probability is determined by the binomial probability formula,

$$\begin{aligned} & \text{Prob(at least 1 event is observed | probability is 1/20)} \\ &= 1 - \binom{N}{n} p^n (1-p)^{N-n} = 1 - \binom{20}{0} p^0 (1-p)^{20-0} = 1 - (1)(1)(.95)^{20} = 1 - .358 \\ &= .64 \text{ or } 64\% \end{aligned}$$

So, if the probability of an AE is 1/20, or 5%, we will have a 64% probability of observing at least one AE in our AM treatment group. To increase the probability to 90% would require  $n = 45$  per group, which is unreasonable. That is, it is more ethical to use fewer subjects at this stage of the product development, in case the risk of an AE is even higher. Furthermore, if the risk of the AE is very high 1/10, or 10%, we have an 88% probability of observing an AE with our  $n=20$ .

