### **Research Design and Methods**

All patients enrolled in the study will undergo the standard procedures as part of the surgical preparation and follow-up. The study is comprised of five main time periods: 1) Pre-operative screening 2) manufacturing and storage of hAM, 3) surgical application/implantation with hAM, 4) follow up and evaluation of postoperative efficacy of hAM, 5) collection and analysis of clinical data.

**Preoperative screening** We will enroll 40 patients undergoing elective coronary artery bypass grafting (CABG). The successfully screened cohort will be randomized to (20 patients in each arm): Interventional arm (patients who will have AM placed epicardially) and control arm (pericardial closure over great vessels and base of right ventricle, leaving the bottom part uncovered).

A pre-surgical echocardiogram will be conducted to evaluate ejection fraction, valvular dysfunction, cardiomyopathy, chamber dimensions, cardiac motion, and strain. Candidate predictor variables (patients' demographic features and clinical risk factors), echocardiographic parameters like atrial dimensions and ejection fraction, CHA2DS2-VASc score, and other patient factors will be collected.

**Inclusion Criteria:** Patients undergoing primary elective CABG at the University of Utah Hospital; Patients 18 years or older; Ability to provide informed consent and follow-up with protocol procedures

**Pre-operative Exclusion Criteria:** Patients in AF at the time of surgery; Prior history of sternotomy; Prior history of pericarditis; Currently on aggressive antiarrhythmic therapy (does not include beta blockers); Patients with an implantable cardiac device (pacemaker, ICD, CRT-D), ejection fraction <45%.

Patients will be randomly assigned 1:1 to the control group or the study treatment group through a computer system, REDCap, to eliminate biased treatment assignments.

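### A favourable trend of unstated size is read as apparent efficacy and as feasibility, yet on POAF counts a bare favourable direction would arise in 42-44% of trials if AM had no effect

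*Combined protocol and SAP*

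**What the plan says.** Research Design and Methods plans "20 patients in each arm" with 1:1 allocation. The Sample Size Justification gives one power statement for the efficacy aims: "This provides 80% power to detect a 0.80 SD difference in means, using a two-sided alpha 0.10 comparison". It then sets significance aside as not needed in a pilot, because "only a trend in the expected direction is required".

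Statistical Methods, under Aims 2 and 3, gives the consequence: "If trends are observed in the expected direction (AM appears to be efficacious), this will support a conclusion of feasibility". The same sentence adds that this justifies moving to the larger study. Chi-square or Fisher tests are planned for binary outcomes and t-tests for continuous ones, but neither is tied to that conclusion.

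The plan does not say how large a trend must be, which Aim 2 or Aim 3 outcome must show it, or how a tie counts. It gives no error rate for concluding from direction, and no power for POAF incidence. Safety (Aim 1) is the primary objective under Specific Aims, but the advancement sentence does not mention it.

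**The concern.** Two separate inferences are drawn from direction.

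The first is efficacy. With 20 patients per arm, chance alone will often put AM ahead. If nothing more is required, an inert membrane will often be described as apparently efficacious, and the plan does not tell the reader how often.

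The second is feasibility. Whether AM had fewer POAF patients says nothing about whether membranes could be placed, chest-tube and blood samples obtained, or daily home EKGs recorded.

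At stake is the reliability of the pilot's statement about moving to a larger trial of an implant. The Aim 1 safety estimates are not affected.

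**Working it through.** **Inputs from the plan.** n = 20 per arm, 1:1 (Research Design and Methods). POAF 20-50% after cardiac surgery (Background and Significance), used here as the range of control rates. Two-sided alpha 0.10 and a difference of 0.80 SD (Sample Size Justification).

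**Assumptions.** POAF incidence is the deciding outcome. The trend is present when the AM count is below the control count, and a tie does not count. All 20 patients per arm are evaluable. The benefit and harm sizes are illustrative, because the plan gives no target POAF reduction.

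**The plan's own figure.** The normal approximation gives Φ(0.80 × √(20/2) − 1.645) = Φ(2.530 − 1.645) = Φ(0.885) = 81.2%. The noncentral t with 38 degrees of freedom gives 79.9%. The stated 80% reproduces, but it describes a significance test on means, which the text then says is not needed.

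**Direction on POAF counts.** Let X be the AM count and Y the control count, independent Binomial(20, p_AM) and Binomial(20, p_C). Then P(trend) = Σ P(Y = i) P(X = j) over all j < i, enumerated exactly.

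With no effect the two directions are equally likely, so P(trend) = (1 − P(tie))/2:

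| POAF in both arms | Tie | Trend present |
|---|---|---|
| 20% | 15.8% | 42.1% |
| 30% | 13.7% | 43.1% |
| 40% | 12.8% | 43.6% |
| 50% | 12.5% | 43.7% |

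For example, at 20%: (1 − 0.158)/2 = 0.421. Counting ties as favourable would raise the range to about 56-58%.

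With an assumed true effect:

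| Control vs AM | Trend present | Trend missed |
|---|---|---|
| 20% vs 10% | 75.0% | 25.0% |
| 30% vs 20% | 71.0% | 29.0% |
| 40% vs 30% | 69.3% | 30.7% |
| 50% vs 40% | 68.5% | 31.5% |
| 30% vs 15% | 83.3% | 16.7% |
| 40% vs 20% | 89.2% | 10.8% |
| 50% vs 25% | 93.5% | 6.5% |
| 30% vs 40% (harm) | 20.2% | n/a |

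At 30% vs 20%, the 29.0% missed is 17.8% in the wrong direction plus 11.2% ties.

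**Direction on a marker mean.** With no effect and equal arms, the difference in means is symmetric about zero, so a favourable sign occurs in 50% of trials if ties are negligible.

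**Precision.** The approximate 90% half-width for the POAF risk difference, with a common rate p, is 1.645 × √(2p(1 − p)/20). At p = 0.2 this is 1.645 × √0.016 = 0.208. At p = 0.5 it is 1.645 × √0.025 = 0.260. The interval is therefore about ±21 to ±26 percentage points.

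**The case against.** The best defence is that the plan sets no mechanical rule. It speaks of trends in the plural across Aims 2 and 3, says they will support a conclusion, and never says that a one-patient difference suffices or that POAF decides alone. That stands, so the percentages are conditional. If any one of several outcomes sufficed, the false-positive rate would be higher. If all had to agree, it would be lower. But nothing in the plan supplies a threshold that would rule out the direction-only reading.

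A second defence is that this is a pilot, that tests and descriptive statistics will accompany any trend, that ease of handling is reported, and that the consequence is another trial and not a change in practice. This limits the harm. It does not justify calling a direction apparent efficacy, or treating it as feasibility.

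Three stronger readings are tempting but unsupported:

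- **The rule is a coin toss in both directions.** That is roughly true with no effect. However, 71% at 30% vs 20%, against 43% with no effect and 20% with harm, is weak discrimination and not none. For a halving from 30-50%, the trend is found in 83-93% of trials.
- **The go/no-go conclusion is the pilot's stated purpose.** Specific Aims makes safety primary and POAF secondary, and the plan also names estimation for sizing the next study.
- **A harmful membrane would advance in one trial in five.** The 20% concerns POAF direction only. The Aim 1 safety results would also be available, although the advancement sentence does not cite them.

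**Conclusion.** The concern holds in a limited form. As worded, the plan lets a trend of unspecified size, with significance waived, stand for apparent efficacy and for feasibility.

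The 42-44% result needs no assumed treatment effect. It does need POAF incidence as the deciding outcome, a strict inequality, 20 evaluable patients per arm, and the background range to apply to these elective CABG patients. The miss rates also depend on the assumed benefit, and the 29% at 30% vs 20% includes 11 points of ties.

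The feasibility part of the conclusion depends on none of these figures: an efficacy direction is simply not a measure of feasibility. The point should be corrected, but it does not undermine the trial's safety objective.

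**What to change.** In Statistical Methods (Aims 2 and 3) and the Sample Size Justification, delete the statements that a favourable trend shows AM appears to work, is all that is required, or supports feasibility. In their place:

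1. Report Aims 2 and 3 as AM-minus-control differences with two-sided 90% intervals, matching the plan's alpha of 0.10. Describe them as estimates for planning the next study, and state the expected POAF precision of about ±21 to ±26 points.
2. Base the advancement statement on the primary Aim 1 safety results and on feasibility counts from data the trial already collects: membranes placed as allocated, scheduled marker samples obtained, and home EKGs recorded. Any targets for these counts are for the sponsor to set in advance.

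A minimum POAF difference is not recommended as a replacement. Requiring at least 3 fewer AM patients, for example, would cut the no-effect rate to 16-21%, but at 30% vs 20% it would miss 57% of trials (1 − 0.428) instead of 29%. That trade-off is the sponsor's judgement.

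The cost is wording only, with no added patients, samples or procedures. The downside is that a small favourable difference could no longer be reported as apparent efficacy.
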